### 6.5. WINDOWING CONVENTIONS

No visit windowing will be performed for this study.

STATISTICAL ANALYSIS PLAN: PROTOCOL V56502 Page 17 of 40

### **6.6. S**TATISTICAL TESTS

The default significance level will be (5%); confidence intervals will be 95% and all tests will be two-sided, unless otherwise specified in the description of the analyses.

Two-sided CIs will be assessed at the 5% significance and two-sided p-value will be reported.

### 6.7. COMMON CALCULATIONS

For quantitative measurements,

- change from baseline will be calculated as Test value at Day x Baseline Value
- percent change from baseline will be calculated as

(Test value at Day x – Test value at Baseline) Test value at baseline X 100

### **6.8. SOFTWARE VERSION**

All analyses will be conducted using SAS version 9.4.

### 7. STATISTICAL CONSIDERATIONS

## **7.1.** Adjustments for Covariates and Factors to be

### **INCLUDED IN ANALYSES**

The following covariates and factors are used in the analyses. For details of their inclusion in the models, see the specific analysis in Section 15.

- Treatment
- Prior anti-TNFα therapy
- Baseline CDAI score

STATISTICAL ANALYSIS PLAN: PROTOCOL V56502 Page 18 of 40

### 7.2. MULTICENTER STUDIES

This study will be conducted by multiple investigators at multiple sites and the summaries will not be presented by site. Randomisation to treatment arms is not stratified by center.

### 7.3. MISSING DATA

Missing safety data will not be imputed while missing dates will be imputed as per appendix 2.

Missing efficacy data will be handled as described in section 15.1.2 of this analysis plan.

### 7.4. MULTIPLE COMPARISONS/ MULTIPLICITY

All statistical comparisons will be made at the 5% level. No adjustment will be made for multiple comparisons. Interpretation of the results should consider this

### 7.5. EXAMINATION OF SUBGROUPS

No subgroup analyses are planned for this study.

### 8. OUTPUT PRESENTATIONS

The templates provided with this SAP describe the presentations for this study and the format and content of the summary tables and listings to be provided by IQVIA Biostatistics.

Tables will be presented by V565, Placebo and Total unless otherwise specified. For efficacy outputs, Total column will not be presented.

### 9. DISPOSITION AND WITHDRAWALS

All subjects who provide informed consent will be accounted for in this study.

Subject disposition including number and percentage of subjects screened, screen failures including reason as entered in "Eligibility" eCRF, randomised, treated, completed the study, discontinued early (including primary reason of discontinuation as mentioned in Disposition Study page of eCRF) will be tabulated by treatment group and Total.

Summaries for overview of disposition will be based on ITT subjects.

Number and percentage of subjects in each population and excluded subjects and the reason for exclusion from each population will also be summarised. Percentages for population exclusion will be based on ITT population.

Subjects who are excluded and reason for exclusion from safety, ITT, PP, PK and Immunogenicity population will be

STATISTICAL ANALYSIS PLAN: PROTOCOL V56502 Page 19 of 40

listed.

Protocol deviations captured by the Clinical Trials Management System (CTMS) will be summarised and listed on ITT population. Percentages will be based on ITT population for protocol deviation summary.

### **10.** DEMOGRAPHIC AND OTHER BASELINE CHARACTERISTICS

Demographic data and other baseline characteristics will be presented for the ITT, SAF and PP populations.

No statistical testing is planned for demographic or other baseline characteristics.

Summaries for continuous and categorical variables (as described in section 6) will be presented for each treatment and Total.

Demographics and baseline characteristics will be presented in a listing by subject.

The following demographic and other baseline characteristics will be reported for this study

- Age (years) at screening as collected from eCRF
- Sex
- Race
- Ethnicity
- Body Weight (kg) at screening
- Height (cm) at screening as collected from eCRF
- BMI (kg/m^2) at screening as collected from eCRF
- Prior Anti-TNF Therapy
- Childbearing potential for female subjects
- Disease duration (months)
- Baseline CDAI score
- Baseline CRP for patients qualifying on CRP
- Baseline FCP for patients qualifying on FCP
- Baseline SES-CD score
- Prior CD medication use

STATISTICAL ANALYSIS PLAN: PROTOCOL V56502 Page 20 of 40

### **11. DISEASE AND MEDICAL HISTORY**

Disease and Medical History information will be presented for the ITT and PP population.

### **12. PREVIOUS IBD TREATMENT/THERAPY HISTORY**

The previous IBD treatment and therapies as captured in the eCRF will be summarised by counts and percentages of subjects and also be listed on ITT population.

### 13. MEDICATIONS

Medications will be presented for the ITT population and coded using WHO Drug dictionary 01Sep2016E. See appendix 2 for handling of partial dates for medications

- 'Prior' medications are medications which started and stopped prior to the first capsule of study drug
- 'Concomitant' medications are medications which:

STATISTICAL ANALYSIS PLAN: PROTOCOL V56502 Page 21 of 40

started prior to, on or after the first capsule of study drug or started before the end of study drug, and ended on or after the date of first dose of study drug or were ongoing at the end of the study drug

• 'Post treatment' medications are medications which are started after the last capsule of study drug and at or before the follow up visit

Concomitant medications will be summarised by ATC level 2 and preferred term based on ITT population. Summary will be presented for each treatment and Total.

Details of prior, concomitant and post treatment medications will be listed.

The following permitted medications based on the preferred term will be summarised by ATC level 2 and preferred term based on ITT population.

- Oral Corticosteroids
- Oral Aminosalicylates
- Methotrexate
- Azathioprine/6-MP
- Oral Antibiotics
- NSAIDs such as low dose aspirin [<325 mg/day]
- Probiotics at an unchanged dose

### **14. STUDY DRUG COMPLIANCE**

Compliance to study drug will be presented for the SAF population.

### **14.1. DERIVATIONS**

Compliance with study drug based on the drug accountability data will be calculated as the number of capsules taken (total dispensed – total returned) divided by the prescribed number of capsules expressed as a percentage, see calculations below.

([Date of Day 42] – [Date of Dispensing at Day 1]+1)\*  $\theta$ 

Where  $\Theta$  = 9, Number of capsules required to be taken per day.

For subjects who discontinued from the study, the "Date of Day x" will be replaced by the date of study discontinuation where x= 14 and 42.

Each subject will be considered non-compliant if taking less than 80% or more than 120% of the expected capsules.

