# 4.0 INVESTIGATIONAL PLAN

### 4.1 Summary of Study Design

This study will be a multiple-site, double-blind, placebo-controlled, parallel-group proof-of-concept study in approximately 126 subjects with active CD. This study will include subjects who have a confirmed diagnosis of CD for at least three months and have CD involving the ileum and/or colon. Inclusion and exclusion criteria are described in detail in Section 4.4.

The duration of treatment will be 42 days (six weeks); each subject's participation in the study will be approximately 12 weeks. This includes a screening period of up to 28 days, a treatment period of 42 days and a follow-up period of 14 days after the last dose of study drug.

Subjects will be randomised into two treatment arms: either V565 or placebo using a 2:1 active:placebo ratio. Randomisation will be stratified to ensure treatment groups have similar rates of prior anti-TNF $\alpha$  therapy.

Subjects will receive three V565 185 mg capsules three times daily or matching placebo, for 42 days (six weeks). The total daily V565 dose is 1665 mg.

Subjects will be treated with study drug as an add-on to any permitted stable medications already being taken for CD. Permitted CD medications are described in Section 5.10.2. No alteration of background CD medication will be permitted for the duration of the study.

There are six study visits. Two screening visits to assess eligibility will occur during Days - 28 to Day -1; these are Visit 1 (start of screening), and Visit 2 (eligibility ileocolonoscopy). Additional study visits will occur on Day 1 (randomisation and initiation of treatment), Day 14 (Interim Visit), Day 42 (End of Treatment Visit), and Day 56 (Follow up Visit).

Collection of subject-reported variables of the CDAI will be via the diaries given to subjects at Visit 1. Prior to Visit 2, the subject-reported variables will be combined with the variables collected at the site on Visit 1 and the CDAI score will be calculated. In order to have an ileocolonoscopy, eligible subjects must have sufficient diary entries to calculate a CDAI score, a CDAI score  $\geq$ 220 to  $\leq$ 450 and a CRP  $\geq$ 5 mg/L (or if CRP is normal, FCP  $\geq$ 250 µg/g) prior to Visit 2.

A previous ileocolonoscopy conducted within 12 weeks before Visit 1 may be substituted for the Visit 2 ileocolonoscopy provided it is forwarded to the central reader and was performed in such a way as to enable evaluation by the central reader.

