### 4.2.5 Early Termination Visit

A subject will have an Early Termination Visit if they discontinue treatment with study drug or withdraw from the study. If a subject withdraws from the study, or is discontinued from treatment with study drug, every effort should be made to complete an Early Termination Visit with the same assessments as scheduled for Day 42. The Early Termination Visit should be scheduled as soon as possible after it has been decided that the subject will be permanently discontinued from treatment with study drug. In addition to the Early Termination Visit, the Follow-up Visit should be performed on Day 56 if possible. Details describing subject withdrawal are presented in Section 4.5.

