# 5.9 Blinding

This is a randomised, double-blind, placebo-controlled study with limited access to the randomisation code. Study drug and placebo capsules will be identical in physical appearance. The treatment each subject will receive will not be disclosed to the Investigator, study site staff, subject, Sponsor, designee or contracting clinical safety laboratories.

Investigators are strongly discouraged from requesting the blind be broken for an individual subject, unless there is a subject safety issue that requires unblinding and would change subject management.

The decision to break the blind in an emergency situation remains the responsibility of the treating physician, which will not be delayed or refused by the Sponsor. However, the Investigator may contact the Medical Monitor prior to breaking the blind to discuss unblinding. The Investigator should promptly notify the Medical Monitor of the emergency unblinding and the reason for breaking the blind, which should be clearly documented. Emergency unblinding should only be performed by the Investigator through the IWRS. In case of unblinding, the subject should be withdrawn from the study (permanently stops the study drug, but attends the Early Termination Visit and Follow-up Visit if possible).

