# % VHsquared

STATISTICAL ANALYSIS PLAN: PROTOCOL V56502

Page 13 of 40

- i. Inclusion criterion 2: CDAI score of ≥220 to ≤450 during Screening
- ii. Inclusion criterion 3: CRP  $\geq$ 5 mg/L (or, if CRP is normal, FCP  $\geq$ 250 µg/g) at screening.
- iii. Inclusion criterion 4: Active CD of ileum and/or colon as determined by the baseline ileocolonoscopy
- b. The following exclusion criteria should be absent in the data for the subjects:
  - i. Exclusion criterion 3: Any gastrointestinal (GI) manifestations of CD that might affect the evaluation of efficacy.
  - ii. Exclusion criterion 5: Prior primary efficacy failure of or secondary loss of response to anti-TNFα therapy, or any contraindication to anti-TNFα therapy
  - iii. Exclusion criterion 6: The use of medications prior to the study or during the study with the potential to affect the evaluation of efficacy.
- 2. Mishandling of the study drug which could have impacted the integrity of the study data such as nonallowable temperature deviations during storage or dispensing of study drug to the wrong subject
- 3. Non-compliance rate of <80% or >120% with study treatment.
- 4. Use of prohibited concomitant medications.
- 5. Study procedures done outside protocol-specified window period that are judged to affect study efficacy data.
- 6. Assessments for primary endpoint not done.

Protocol deviations will be reviewed prior to unblinding and individual subjects having protocol deviations will be evaluated for inclusion in the PP population. Any additional deviations not listed above will be documented at this time.

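### SAP 14.1 ends the compliance denominator for early leavers at an undefined study discontinuation date, so days after drug was stopped can count as missed doses; the matching per-protocol item is also worded in reverse

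*SAP*

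**What the plan says.** SAP 14.1 takes the number of capsules used (dispensed minus returned), "divided by the prescribed number of capsules expressed as a percentage". The prescribed number is the days from dispensing at Day 1 to the visit date, inclusive, times 9, the "Number of capsules required to be taken per day". For subjects who discontinued from the study, the Day 14 or Day 42 date "will be replaced by the date of study discontinuation". The cut-off follows: "Each subject will be considered non-compliant if taking less than 80% or more than 120% of the expected capsules".

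SAP 5.2 lists the major deviations that remove a subject from the per-protocol (PP) population. Item 3 reads "Non-compliance rate of <80% or >120% with study treatment". The same section says that subjects with deviations are considered individually before unblinding. SAP 15.1.4 repeats the primary model on the PP population as a sensitivity analysis; SAP 15.1.3 puts the primary analysis on ITT.

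On the timing of stopping, Protocol 4.2.5 names stopping study drug and withdrawing from the study as alternatives. It asks for an Early Termination Visit as soon as possible, sets no maximum delay, and continues: "In addition to the Early Termination Visit, the Follow-up Visit should be performed on Day 56 if possible". Protocol 5.9 describes an unblinded subject as one who "permanently stops the study drug, but attends the Early Termination Visit and Follow-up Visit if possible". Protocol 6.1.2 asks subjects who stop treatment early to keep recording CDAI data until the Early Termination Visit.

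**The concern.** Nothing is prescribed once drug has been permanently stopped. If the date entered as study discontinuation is the Early Termination Visit or a later contact, each day after the stop adds 9 capsules to the denominator that the subject was never due to take. This can only lower the computed figure, and only for early leavers.

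Two outputs use the result. The compliance summary for the safety population (SAP 14) would read low for early leavers. The 80% limit is also a listed ground for PP exclusion, so a subject who took every capsule up to an early stop could be flagged as non-compliant. The item for primary assessments not done (SAP 5.2 item 6) need not remove the same subjects anyway: the Early Termination Visit carries the Day 42 assessments (Protocol 4.2.5), and SAP 6.4 reports it together with Day 42. The compliance flag can therefore be what decides PP membership.

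The wording of SAP 5.2 item 3 is a second problem that does not depend on any gap. It applies the 80% and 120% limits to a rate of non-compliance, whereas SAP 14.1 applies them to capsules taken.

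**Working it through.** **Inputs.** Three capsules three times daily for 42 days (Protocol 4.1: "Subjects will receive three V565 185 mg capsules three times daily or matching placebo, for 42 days"); 9 capsules per day and the 80% limit (SAP 14.1); 126 randomised as 84:42 and about 114 completing as 76:38, at 10% dropout (Protocol synopsis). The gap between last dose and study discontinuation is not in the documents, so it is varied below as an assumption.

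**The plan's own figure.** 3 × 3 = 9 capsules per day, and 9 × 185 mg = 1665 mg, the stated daily dose. A full course is 42 × 9 = 378 capsules. The SAP's multiplier is reproduced.

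**Formula for an early leaver.** Let a subject take every capsule from Day 1 to day D, with study discontinuation recorded g days later.

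- Capsules taken = 9D.
- Prescribed under SAP 14.1 = 9 × [(D + g) − 1 + 1] = 9(D + g).
- Computed compliance = 9D / 9(D + g) = D / (D + g).
- This is below 0.80 when D < 0.8D + 0.8g, that is, when g > D/4.

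| Last dose, day D | D/4 | Smallest whole-day gap giving <80% | Compliance at that gap | Compliance at an assumed 7-day gap |
|---|---|---|---|---|
| 7 | 1.75 | 2 | 7/9 = 77.8% | 7/14 = 50.0% |
| 14 | 3.5 | 4 | 14/18 = 77.8% | 14/21 = 66.7% |
| 21 | 5.25 | 6 | 21/27 = 77.8% | 21/28 = 75.0% |
| 28 | 7 | 8 | 28/36 = 77.8% | 28/35 = 80.0% (not below) |
| 35 | 8.75 | 9 | 35/44 = 79.5% | 35/42 = 83.3% |

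Shorter gaps do not trigger the flag: at D = 14 and g = 3 the figure is 14/17 = 82.4%. At g = 0 it is D/D = 100% for every D. If the denominator ends at day D, it is 9D/9D = 100% whatever the gap.

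**How many subjects.** 126 − 114 = 12 planned early leavers (84 − 76 = 8 on V565, 42 − 38 = 4 on placebo), in line with 126 × 0.10 = 12.6. This counts all planned dropouts. Those affected are only the ones whose gap is long enough, so about 12 is a ceiling at the planned dropout rate.

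**SAP 5.2 item 3 against SAP 14.1.** Take a subject who missed 5% of capsules. Under SAP 14.1 compliance is 95%, which is acceptable. Under the literal text of item 3 the non-compliance rate is 5%, which is below 80%, so the subject meets the exclusion item. If the rate means the share of capsules missed, it also cannot exceed 100%, so the 120% limit could never apply. The two sections give opposite answers for the same subject.

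**The case against.** A reader might infer that fully compliant subjects who stop early will be computed as below 80% and dropped from the PP analysis. The documents do not support that. They give no gap and do not say which date is recorded as study discontinuation. Protocol 4.5 treats withdrawing from the study as permanently stopping drug, and the Protocol 5.9 wording can be read the same way, with the later visits following the withdrawal. If the recorded date is the stop date, the gap is zero and the formula is right.

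It is also tempting to take Day 56 as the end date, which would give 14/56 = 25.0% for a stop at day 14. Nothing says that the follow-up visit is recorded as discontinuation. Nor do the documents show that gaps would differ by arm; imbalance is possible but is not demonstrated.

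Exclusion is not automatic either. SAP 5.2 provides for individual review before unblinding, and SAP 5 leaves further detail to a separate review plan. Some early leavers would leave the PP set anyway, for prohibited medication or missing primary assessments. These points stand, and they limit the finding to something that can happen.

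They do not remove it. Protocol 4.2.5 and 6.1.2 both allow an interval between stopping drug and the Early Termination Visit. The SAP also keeps the two events apart: SAP 9 takes discontinuation from the study disposition page, while SAP 17.1.2 deals with discontinuation of study drug. Blinded review would be working from the wrong figure, and no such review is described for the compliance table.

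A further objection is that ending at last dose lets a subject treated for 7 of 42 days score 100%. That is already so under the SAP formula when there is no gap, so the change adds no new PP policy. On item 3, a programmer would probably follow SAP 14.1, but the conflict should not be left to that.

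**Conclusion.** The point holds as a minor ambiguity with a possible downward error. An early leaver who took every capsule can be computed as below 80% if study discontinuation is dated more than a quarter of the treated days after the last dose. For a stop within the first two weeks a gap of 4 days or fewer is enough; at four weeks it takes 8. Whether this happens depends on two things that the documents do not give: the definition of the date and the length of the gap.

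The reach is at most about 12 of 126 subjects at the planned dropout. Only the safety-population compliance table and the PP sensitivity analysis are exposed, the latter subject to blinded review. The ITT primary analysis does not use compliance. The reversed wording in SAP 5.2 item 3 rests on no assumption: it contradicts SAP 14.1 as written.

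**What to change.** In SAP 14.1, for subjects who stop early, end the denominator at the date study drug was permanently stopped, or at the date of the last capsule where no separate stop date is recorded, in place of the date of study discontinuation. In SAP 5.2 item 3, write: *Compliance <80% or >120% of expected capsules*, so that it matches SAP 14.1.

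The cost is two wording changes, to be made before unblinding. SAP 13 and Appendix 2 already classify medications against the last capsule or end of treatment, so a date of this kind is needed in any case; how completely the eCRF captures it should be confirmed. There is one small downside. Where the last-capsule date is used, doses missed just before formal discontinuation no longer count as non-compliance, which is why a recorded stop date should be preferred.

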#### 15. **EFFICACY OUTCOMES**

#### 15.1. **PRIMARY EFFICACY**

#### 15.1.1. **PRIMARY EFFICACY VARIABLE & DERIVATIONS**

The primary efficacy variable is Responders at Day 42

A Responder is defined as subjects achieving both CDAI ≥70-point reduction from Baseline OR CDAI score <150, and a reduction of  $\geq$ 40% from the baseline value of CRP (where CRP at baseline => 5mg/dL) or FCP (where CRP at baseline <5mg/dL and FCP at baseline =>250 ug/g)

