### Criteria for evaluation:

Primary Efficacy Endpoint:

 Proportion of responders at Day 42, defined as subjects achieving both CDAI ≥70-point reduction from Baseline OR CDAI score <150, AND a reduction of ≥40% from the baseline value of CRP or FCP

Secondary Efficacy Endpoints:

- Proportion of subjects achieving a ≥100-point reduction in CDAI score and a concomitant reduction of 50% in CRP or FCP at Day 42
- Proportion of subjects achieving a  $\geq$ 70-point reduction in CDAI score at Day 42
- Proportion of subjects achieving a  $\geq$ 100-point reduction in CDAI score at Day 42
- Proportion of subjects achieving a CDAI score of <150 CDAI at Day 42
- Changes from Baseline in scores for PRO-2 at Day 14 and Day 42

Safety Endpoints:

• Evaluations of AEs, clinical laboratory results, physical examination findings, ECGs and vital signs throughout the study

Pharmacokinetic Endpoint:

• Serum and urine concentration of V565 prior to first administration of study drug and at Day 14, Day 42, and Day 56. In addition, On Day 1, a post-dose urine sample will be obtained at the site 4 to 8 hours after the first dose of study drug.

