#### AND

• A reduction of ≥40% from baseline value of C-reactive protein [CRP] or faecal calprotectin [FCP])

will be higher in subjects who receive V565 than in subjects who receive placebo when used in combination with their permitted background CD medications.

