# 5.10 Prior and Concomitant Treatments

All medications (prescription and non-prescription), treatments, and therapies taken by the subject from the time consent is signed throughout their entire participation in the study, including those initiated prior to the start of the study, must be recorded on the subject's source document and on the appropriate page of the eCRF. The dose, unit, frequency, route, indication, date the medication was started, and date the medication was stopped (if not ongoing) must be recorded.

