### 5.10.2 Permitted Medications

Medications considered necessary for the safety and well-being of the subject may be permitted during the study at the discretion of the Investigator provided they are not listed as a prohibited medication in Section 5.10.3.

- Background CD Therapy: Subjects will remain on their background CD therapy throughout the study. It should be noted that the doses of background concomitant medications given for the treatment of CD may not be changed during the study. No new background CD therapy may be added to the subject's treatment regimen after Visit 1.
- Oral Corticosteroids:
- Oral Aminosalicvlates:
- Methotrexate:
- Azathioprine/6-MP:
- Oral Antibiotics:
- NSAIDs such as low dose aspirin [<325 mg/day] may be continued at an unchanged dose.
- Probiotics may be continued at an unchanged dose.

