### 5.10.3 Prohibited Medications

The use of the following medications either alone or in combination for the treatment of CD is prohibited **during the study.** 

- Local use (enema or suppository) of 5-ASA
- Corticosteroid administered IV, IM, SC or rectally. (Note: topical use [e.g., inhaled, nasal, aural or ocular] of corticosteroid is allowed during the study.)
- Use of other immunosuppressant agents (other than those permitted as per Section 5.10.2) or therapy (e.g., apheresis) including, but not limited to, cyclosporine, tacrolimus, sirolimus or mycophenolate mofetil
- Anti-TNFα therapy other than the study drug.
- Any other biological therapy for IBD.

- Parenteral or enteral nutrition therapy.
- Chronic use of NSAIDs other than for cardioprotection (as detailed in Section 5.10.2).
- Chronic use of opioids (e.g., codeine, fentanyl, tramadol, etc.).
- Vaccination with live, attenuated, or recombinant vaccines.

**Note**: Subjects should not discontinue prohibited pre-existing background CD medications prior to Visit 1 in order to qualify for the study.

The use of any prohibited medication is considered a protocol deviation and the details including the starting date and its dosage should be recorded in the eCRF. Subjects should be withdrawn from the study if any prohibited medications are taken or if background CD therapy is changed during the study.

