### 8.2.1 Primary Efficacy Analysis

The primary clinical efficacy endpoint of the study is the proportion of subjects at Day 42 that have both CDAI  $\geq$ 70-point reduction from Baseline or CDAI <150, *and* a reduction of  $\geq$ 40% from the baseline value of CRP or FCP.

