## 🕉 VHsquared

STATISTICAL ANALYSIS PLAN: PROTOCOL V56502 Page 24 of 40

proportion of subjects achieving response to therapy.

The primary efficacy analysis will be performed on ITT population. The primary endpoint will be analysed using a logistic regression model with treatment as the fixed effect and prior anti-TNF $\alpha$  therapy and baseline CDAI score as covariates. For the active treatment versus placebo comparison, the results will be presented in terms of an odds ratio together with its associated 95% CI and 2-sided p-value. Two-sided 95% CIs for the odds ratio will be provided.

The SAS® procedure GENMOD that will be used is given in appendix 3The CDAI score, FCP, CRP results along with the change from baseline values will also be listed and summarised for the ITT population.

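### No visible rule scores a subject as a non-responder after prohibited, newly started or increased Crohn's therapy, so such a subject could count as a responder in the primary ITT analysis

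*SAP*

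**What the plan says.** **Endpoint.** SAP 15.1.1 reads "A Responder is defined as subjects achieving both CDAI ≥70-point reduction from Baseline OR CDAI score <150" and adds a reduction of at least 40% in CRP, or in FCP for subjects who qualified on FCP. The Protocol synopsis has "Proportion of responders at Day 42, defined as subjects achieving both CDAI ≥70-point reduction from Baseline OR CDAI score <150" and Protocol 8.2.1 has "The primary clinical efficacy endpoint of the study is the proportion of subjects at Day 42 that have both CDAI", each with the same thresholds. Protocol 2.3 uses the same two conditions and places the comparison in subjects treated "when used in combination with their permitted background CD medications".

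**Analysis set.** "The primary efficacy analysis will be performed on ITT population" (SAP 15.1.3). SAP 5.1 defines this set as everyone randomised.

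**Conduct.** Protocol 5.10.2 states that "the doses of background concomitant medications given for the treatment of CD may not be changed during the study" and bars new CD therapy after Visit 1. Protocol 5.10.3 adds: "Subjects should be withdrawn from the study if any prohibited medications are taken or if background CD therapy is changed during the study".

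**Data after withdrawal.** Protocol 4.2.5 asks for an Early Termination (ET) visit with the Day 42 assessments, and 6.1.2 asks for CDAI recording up to that visit. SAP 6.4 reports Day 42 and ET as one visit in by-visit summaries. SAP 15.1.2 treats responder status as missing when CDAI or CRP/FCP is missing. SAP 6.3 fills gaps by last observation carried forward (LOCF) from the last post-baseline visit.

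**Sensitivity analyses.** SAP 15.1.4 repeats the model with worst observation carried forward (WOCF) and on the per-protocol (PP) set. The grounds for PP exclusion in SAP 5.2 include prohibited concomitant medication (item 4) and medication before or during the study that could affect the efficacy evaluation (item 1.b.iii). The list is open.

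**The concern.** The hypothesis is about V565 added to background CD therapy that stays fixed. Added or increased CD therapy can itself lower CDAI and CRP/FCP, so a response scored after it is not clearly a response to study drug. The plan takes the same view: it withdraws these subjects and lists such medication among deviations that affect the primary analysis. Yet nothing visible carries that view into the primary score. More such use on placebo would shrink the observed difference, and more on V565 would enlarge it.

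**Working it through.** **Step 1. The four endpoint statements side by side.**

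| Place | CDAI condition | CRP/FCP condition | Medication condition |
|---|---|---|---|
| Protocol synopsis | yes | yes | none |
| Protocol 2.3 | yes | yes | none (background therapy is the setting, with no score attached) |
| Protocol 8.2.1 | yes | yes | none |
| SAP 15.1.1 | yes | yes | none |

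**Step 2. How a subject given forbidden CD therapy gets a score.**

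| Case | Values used in the primary analysis | WOCF repeat | PP repeat |
|---|---|---|---|
| A. Not withdrawn, contrary to 5.10.3 | observed Day 42 | same score | can be excluded |
| B. Withdrawn, ET stands in for Day 42 | ET | same score | can be excluded |
| C. Withdrawn, Day 42 treated as missing | LOCF from last post-baseline visit | non-response | can be excluded |

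The visible text does not settle B against C. In both, the values may wholly or partly predate the new drug.

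**Step 3. Why WOCF closes case C only.** WOCF draws on baseline as well as later values (SAP 6.3), and baseline CDAI is the screening score (SAP 6.2), so b ≥ 220 for an eligible subject. The worst value w satisfies w ≥ b. Then b − w ≤ 0, which is not a 70-point fall, and w ≥ 220, which is not below 150. The CDAI condition fails. If only CRP/FCP is missing, its worst value is at or above baseline, so the reduction is at most 0% and the 40% condition fails. In A and B nothing is missing, so WOCF does nothing.

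**Step 4. Size.** Inputs from the Protocol synopsis: 126 randomised (84 V565, 42 placebo), 10% dropout, 114 completers (76:38). Check: 126 × 0.9 = 113.4; 84 × 0.9 = 75.6, rounded to 76; 42 × 0.9 = 37.8, rounded to 38. The plan's figures are reproduced. Planned dropouts are 84 − 76 = 8 and 42 − 38 = 4, which is 9.5% of each arm.

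One reclassified subject moves the placebo rate by 1/42 = 2.4 points or the V565 rate by 1/84 = 1.2 points. If k_p placebo and k_v V565 responders become non-responders, the crude difference V565 minus placebo changes by 100 × (k_p/42 − k_v/84). The documents give neither count, so those below are assumptions within the planned dropout numbers.

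| k_p | k_v | Change (points) |
|---|---|---|
| 1 | 2 | 0.0 |
| 1 | 0 | +2.4 |
| 2 | 0 | +4.8 |
| 0 | 2 | −2.4 |
| 0 | 4 | −4.8 |
| 4 | 0 | +9.5 |
| 0 | 8 | −9.5 |

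The last two rows are the extremes for withdrawn subjects at the planned dropout. They need every dropout in one arm, and none in the other, to have changed CD therapy and been scored a responder. Case A is not limited by the dropout figure.

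**The case against.** **Text is missing where a rule could stand.** Protocol 3.2.1 (the formal endpoint section) and 4.3 are in the contents list but not in the available text. Parts of Protocol 5.10.2 and 8.2.1 are absent. SAP 15.1.1 lacks the CDAI derivation that SAP 15.3.1.2 says is there. SAP 15.1.2 stops where its LOCF criteria should begin, and the blinded data review plan is a separate document. This stands, and it limits the claim to the visible text. A hidden rule looks less likely, because the synopsis gives the primary model without one and SAP 3.3, which lists changes from the protocol, mentions none. Neither fact excludes it.

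**The plan already handles such use.** A reader might infer that the plan ignores it. It does not: changes are forbidden, users are to be withdrawn, and PP items 4 and 1.b.iii can exclude them. But withdrawal assigns no score, and the PP repeat drops these subjects instead of counting them as failures. The primary result is unchanged.

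**The exposed cases are narrow.** A needs a departure from 5.10.3, B needs the by-visit convention of SAP 6.4 to govern the responder derivation, and C is covered by WOCF. ET visits are to be held promptly, which limits time on the new drug, and a Day 14 value from before the new drug is not contaminated by it. All of this reduces exposure. It does not remove it: in C, a subject who met the criteria at Day 14 and later needed more therapy could still count as a Day 42 responder in the primary analysis.

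**Scoring everyone on measured values is a legitimate ITT choice.** It is, and non-response scoring answers a somewhat different question. That question is closer to Protocol 2.3, and the current scoring can be kept alongside.

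**Conclusion.** The gap is real on the visible text: no endpoint statement and no visible imputation rule prevents a subject given forbidden CD therapy from being scored a responder in the primary ITT analysis. The conclusion assumes that the unseen sections contain no such rule.

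A reader might infer that the primary result is biased, perhaps towards V565, or that power is materially lost. The documents do not support that. They give no rate of medication change, the direction depends on which arm has more of it, and the response rates behind the sample size are not visible, so power cannot be recomputed. The per-subject steps of 2.4 and 1.2 points are firm for arms of 42 and 84. The ±9.5-point extremes are arithmetic limits, not expectations. All are crude differences in proportions, whereas the primary model reports an adjusted odds ratio. Severity is low to moderate.

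**What to change.** Unless the unseen text already does this, add to SAP 15.1.1, and to 15.2.1 for the binary secondary endpoints:

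> A subject who, after the screening CDAI assessment (Visit 1) and up to the Day 42 assessment, takes a CD treatment prohibited by Protocol 5.10.3, or starts or increases a background medication for CD beyond what Protocol 5.10.2 permits, is a non-responder whatever the observed, Early Termination or carried-forward values.

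The window should open at Visit 1, not at first dose. Baseline CDAI is the screening score and new CD therapy is barred from Visit 1, so therapy added between screening and first dose could lower Day 42 CDAI against that baseline.

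Flag these subjects at the blinded data review planned in SAP 5. The data needed are already collected: "The dose, unit, frequency, route, indication, date the medication was started, and date the medication was stopped (if not ongoing) must be recorded" (Protocol 5.10). Keep the current scoring as a sensitivity analysis.

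The cost is one SAP sentence, one derived flag and some blinded review work. Response rates may fall slightly. The endpoint becomes response without added CD therapy, so unequal use between arms then counts as part of the treatment difference and is not removed from it.
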